7.3.2 Statistical analyses

All analyses will be conducted with a modified intention to treat approach, which excludes randomized participants who were found on testing to have an undetectable HCV RNA, HBsAg positive or a platelet count <150,000. Our primary analysis will be logistic regression analyses. Statistical inference will use a two-sided Type 1 error rate of 0.05 and 95% confidence intervals.

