2 INTRODUCTION

2.1 Background and Rationale

[figure not shown]
Why Is This Study Being Conducted?

Hepatitis C virus (HCV) infection is a major public health challenge and is associated with significant morbidity and mortality.¹ The World Health Organization (WHO) has called for elimination of HCV as a public health challenge by the year 2030. The WHO elimination goals include a 90% reduction in HCV incidence and a 65% reduction in HCV related mortality by 2030 relative to 2015 rates.² However, the United States is experiencing increases in HCV incidence directly attributable to injection drug use with the steepest increase in incidence since 2011.^{3,4} Although people who use drugs (PWUD) have disproportionately high rates of HCV infection, rates of HCV treatment remain low among PWUD.^{5,6} Once initiated on HCV therapies, PWUD have been demonstrated to achieve high rates of HCV cure.⁷

HCV treatment uptake among PWUD, the core of the HCV epidemic, remains low due to multiple interrelated barriers at the level of the patient, the provider, and the system.⁸⁻¹⁰ Patient-level barriers include poor knowledge related to HCV and its treatment and absence of symptoms. These issues are compounded by general barriers to health care access (e.g., not having insurance or a primary care provider), competing comorbidities, which may require more immediate attention, and factors that impede stability, such as ongoing Substance Use Disorder (SUD), unemployment, and lack of transportation.¹¹⁻¹³ In many parts of the world, the major structural barrier of medication cost has been reduced through insurance coverage for HCV treatment by payers and removal of insurance coverage restrictions related to drug use or liver disease stage. Beyond cost, additional structural barriers include insufficient HCV treatment locations. HCV care has historically been delivered in specialist settings thus segregating HCV treatment from other services that PWUD utilize including those received at opioid treatment programs (OTPs).

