3.2 Primary Endpoint

The primary effectiveness endpoint is:

Treatment initiation: Proportion of participants who start HCV treatment (in initial test and treat arm versus standard of care referral arm) within 12 weeks of randomization.

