4.2 Study Procedures

4.2.1 Hepatitis C Diagnosis and Recruitment Screen

Prior to study roll out, site investigators will meet with drug treatment center leadership to outline procedures for offering study participation to drug center clients. The OTP will facilitate HCV antibody testing and/or HCV RNA testing through rapid testing or phlebotomy. Prior to study enrollment, participants will complete an initial screening questionnaire, which will explore if the participant has previously been diagnosed with HCV, and if previously diagnosed, previously treated for HCV with oral direct-acting antiviral (DAA) therapy. Individuals who report previous HCV treatment with oral DAA therapy will not be eligible for study enrollment. Potential participants will also be asked about their current medications to ensure they are not currently taking any medication prohibited by the study (see Sections 5.1 and 5.3). Individuals who report taking a study-prohibited medication will not be eligible for study enrollment. These screening questions will be mixed with other questions to ensure that participants remain unaware of study eligibility criteria. Individuals who are HCV antibody or HCV RNA positive on testing and remain study eligible after completing the screening questionnaire will be offered enrollment into the study and if willing, go through the process of informed consent.

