7 STATISTICAL METHODS & DETERMINATION OF SAMPLE SIZE

7.1 Statistical and Analytical Plans

The primary analysis for the effectiveness of the test and treat strategy versus standard of care referral for HCV treatment initiation will be assessed using a logistic regression model and a two-sided Type 1 error rate (alpha) of 0.05. Since participants will be recruited from drug treatment programs at which they are receiving ongoing treatment for substance use disorder, we expect low rates of lost to follow up (10%).

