7.3 Statistical Analyses

7.3.1 Primary Analysis

Sample Size and Power Consideration Estimation

The planned sample size for the trial is 124 participants enrolled and randomized in a 1:1 ratio to test and treat strategy versus Standard of Care referral. This sample size is based on preliminary data from the CHAMPS study, which offered free onsite HCV treatment to HIV infected patients at an urban infectious disease clinic and achieved a 70% HCV treatment initiation rate.¹⁵ Data from community-based sites including the AIDS linked to the intravenous experience study suggest an HCV treatment start rate of 30% among community based people who use drugs enrolled in the oral DAA era in Baltimore²¹. Given differences in HCV treatment policies and restrictions, HCV treatment rates were estimated to be up to 55% in other cities prior to the COVID-19 pandemic. HCV treatment uptake rates reduced during and post-COVID 19. We estimate HCV treatment uptake between 30-50% in different cities, averaging 40%. Using these data points as estimates for treatment initiation in the test and treat arm (70%) and the treatment uptake in the referral arm (40%) power calculations are as follows. With a total sample size of 124 participants, we have 85% power at an alpha of 0.05 to detect a statistically significant difference in treatment initiation in the test and treat strategy versus the standard referral arm. The sample size of 124 allows for 110 completers should there be a ~10% drop out rate. If there is no drop out then the total enrollment of the HCV infected participants will be 124. We continue to expect that the treatment uptake will be 70% with the proposed test and treat interventions. Our proposed sample size of 55 completers per group (62 per group including possible drop outs) is adequate to distinguish between the hypothesized 70% uptake and the 40% non-intervention arm uptake with 85% power at the $p = 0.05$ threshold.

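### The primary analysis is specified only as logistic regression, with no OTP site term, no baseline covariate and no effect measure, so its default output is an unadjusted odds ratio for a trial sized on a difference in proportions

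*Combined protocol and SAP*

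**What the plan says.** Section 3.2 defines the primary endpoint as a proportion: "Treatment initiation: Proportion of participants who start HCV treatment", counted within 12 weeks of randomisation. Section 7.1 says the comparison will be made "using a logistic regression model and a two-sided Type 1 error rate (alpha) of 0.05". Section 7.3.2 adds "Our primary analysis will be logistic regression analyses" and "Statistical inference will use a two-sided Type 1 error rate of 0.05 and 95% confidence intervals". That is the whole specification. No section names a covariate, a site term, or the quantity to which the 95% interval belongs.

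Section 7.3.1 sizes the trial on 70% uptake with test and treat against 40% with referral. It explains the 40% as follows: "We estimate HCV treatment uptake between 30-50% in different cities, averaging 40" per cent. Section 4.2.8 allocates 1:1, with a separate randomisation at each OTP.

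Baseline information bearing on uptake is collected:
- The screening questionnaire in 4.2.1 is one "which will explore if the participant has previously been diagnosed with HCV".
- The first exploratory endpoint in 3.4 takes 30-day self-reported drug use and urine toxicology at recruitment screening.
- Appendix A shows urine toxicology and the study survey at Day 0.
- Section 2.1 lists, among the barriers to care, "factors that impede stability, such as ongoing Substance Use Disorder (SUD), unemployment, and lack of transportation".

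**The concern.** Three choices that fix the primary result are left open: which baseline variables enter the model, whether the factor that structures randomisation is one of them, and on what scale the effect is reported. A logistic model fitted to arm alone directly returns an odds ratio. Both design rates are far from rare, so that odds ratio is numerically far from the ratio of uptake and is not the difference used for sizing.

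Two things are at stake. Precision that the trial could have from data it already collects is not claimed. And in an open-label trial, covariates and scale that are not fixed in advance can be chosen after outcomes are known.

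**Working it through.** **1. Reproduce the plan's figure.** Inputs from 7.3.1: p1 = 0.70, p2 = 0.40, two-sided alpha 0.05, power 85%, 55 completers per arm, about 10% dropout.
- Uncorrected n per arm = [1.96·√(2·0.55·0.45) + 1.036·√(0.21 + 0.24)]² / 0.30² = 47.8, so 48.
- Continuity-corrected n = (47.8/4)·[1 + √(1 + 4/(47.8·0.30))]² = 54.3, so 55 per arm, 110 in total.
- 110/0.90 = 122.2, so 123, or 124 as an even total.
- Power at 55 per arm: 85.5% continuity-corrected; 84.6% for Fisher's test by exact enumeration.

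The stated 85% and 124 reproduce.

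**2. Power of the model as written.** Log odds ratio = ln 3.5 = 1.253. SE = √[1/(55·0.21) + 1/(55·0.24)] = 0.403. Wald power = Φ(1.253/0.403 − 1.96) = 87.5%; exact enumeration gives 88.7%. Neither is below the plan's 85%.

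**3. What would be reported at the design rates, 55 per arm.**
- Odds ratio = (0.70/0.30)/(0.40/0.60) = 3.5, 95% CI 1.59 to 7.71.
- Ratio of uptake = 0.70/0.40 = 1.75.
- Risk difference = 30 points; half-width 1.96·√(0.45/55) = 17.7, so 12.3 to 47.7.

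**4. Gain from site, using the plan's city range.** Share of outcome variance explained in the referral arm, R² = Var(site rates)/(0.40·0.60):
- Five sites spread evenly over 30% to 50%: 0.005/0.24 = 0.02.
- All sites at 30% or 50%: 0.01/0.24 = 0.04.

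Using the approximation that adjustment scales the variance by 1 − R², pooled power rises from 89.6% to 90.2% (R² = 0.02) or 90.8% (R² = 0.04). The half-width falls from 17.7 to 17.6 or 17.4 points. In simulation (3,000 trials per setting, five equal sites, arms balanced within site), adding site raised power from 88.3% to 89.7%, and by 1.3 to 1.6 points across the settings with a site effect. With no site effect the change was 0.5 points. Because arms were balanced within site, the gain comes through the standard error. The spread of the risk difference itself was 0.0926 unadjusted and 0.0932 standardised, the latter from a model that also carried a covariate with no effect.

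**5. Gain from further covariates.** The documents give no prognostic strength for drug use or prior diagnosis. Two sets of simulations assumed binary covariates, marginal rates held at 70% and 40%, 55 per arm and likelihood-ratio tests:

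| Assumed covariates | 2,500 trials | 2,000 trials |
|---|---|---|
| One, odds ratio 2 | 88.4 to 89.8% | 89.6 to 90.6% |
| One, odds ratio 3 | 88.9 to 91.9% | 89.7 to 92.7% |
| Two, odds ratio 3 | 88.4 to 92.3% | 90.0 to 93.2% |

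The gains are 1.0 to 3.9 points. In the 2,500-trial set the SE of the risk difference fell from 0.0912 to 0.0866 (5%) with two covariates. Monte Carlo SE of each power in that set is about √(0.89·0.11/2,500) = 0.6 points.

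**6. Why covariates and scale must be settled together.** With marginal rates held at 70% and 40%, the true adjusted odds ratio is 3.6 with site alone, 4.2 at R² of about 0.13 and 4.8 at about 0.20. The standardised risk difference stays at 0.30 throughout.

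**7. The two readings of the city rates.**

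| Referral rate | On-site 70% everywhere: OR; difference | Constant OR 3.5: on-site rate; difference |
|---|---|---|
| 30% | 5.44; 40 points | 60%; 30 points |
| 40% | 3.50; 30 points | 70%; 30 points |
| 50% | 2.33; 20 points | 78%; 28 points |

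**The case against.** The documents are silent; they do not choose. Nothing says that the model is unadjusted or that an odds ratio is the estimate, and a logistic model can be both adjusted and standardised. Section 3.2 and the effectiveness row of Table 1 are framed as proportions by arm, so reporting those proportions is probably intended. This stands: the fault is missing specification.

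An odds ratio of 1 and a risk difference of 0 are the same null hypothesis. A reader might infer that the sample size is undermined; steps 1 and 2 show that it is not.

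A reader might also infer that no single odds ratio can hold across cities. That needs 70% on-site uptake in every city, whereas 7.3.1 gives 70% as one overall expectation. A constant odds ratio of 3.5 gives on-site rates of 60%, 70% and 78%, averaging about 69%, which fits the plan equally well. If on-site uptake were 70% everywhere, the risk difference would vary too. Heterogeneity does not by itself decide the scale; the match to endpoint and sizing does.

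The covariates also need care:
- Section 2.1 lists substance use as a general barrier. Everyone enrolled attends a drug treatment program, so that line does not show that drug use separates starters from non-starters here.
- The urine panel in 5.9 includes methadone and opiates, and OTPs dose opioid agonists, so a positive result would need defining.
- Appendix A places toxicology, survey and randomisation on Day 0 without an order.
- Prior diagnosis is asked before consent, and nothing says the answer is kept.

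These points narrow the choice of covariates. They do not answer the absence of site, the one baseline factor with both a role in randomisation and prognostic figures in the plan.

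**Conclusion.** The point holds as under-specification that should be corrected. Read literally, 7.1 and 7.3.2 give an unadjusted odds ratio of about 3.5 at the design rates, against a ratio of uptake of 1.75 and a difference of 30 points. The test and the 85% power stand. The documents do not support saying that the sponsor chose to omit covariates, that the sizing fails, or that the odds ratio must differ by city.

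The precision at issue is modest: about 1 to 2 power points from site, resting on the plan's 30% to 50% range and an assumed spread of sites across it. Another 1 to 4 points or so from one or two further covariates assumes odds ratios of 2 to 3. The firmer part, which needs no such assumption, is that the primary estimate is undefined and its default scale differs from that of the endpoint and sizing.

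**What to change.** In 7.3.2:
- Fit the logistic model with arm, OTP site and one named drug-use covariate: 30-day self-reported use taken at recruitment screening, before allocation. Align Appendix A with 3.4 so that this timing is explicit.
- Add prior HCV diagnosis only if the screening questionnaire answer is retained as study data.
- Report the standardised (marginal) risk difference with its 95% confidence interval as the primary estimate. Give the odds ratio and the unadjusted difference as supporting results.
- Fix in advance a rule for a missing baseline value and for sites too small to support their own term. With 110 completers over five sites the average is 22 per site.

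Use the same form for SVR12 in 7.3.3. The change costs a few sentences and a few lines of code, with no added participants or visits. The small downside is having to write the two rules.

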7.3.3 Secondary outcomes

- 1) HCV treatment completion: Proportion of those initiating treatment who complete HCV treatment defined as taking more than 90% of prescribed treatment course by expected end of treatment date.
- 2) SVR 12: Proportion of participants with HCV RNA <15 IU/ml between 10 and 36 weeks after end of treatment in each randomization arm.

Analysis for secondary outcomes 1 and 2 will be logistic regression analyses.

- 3) Time to HCV treatment initiation after randomization.

For secondary outcome 3, a time to event outcome, we will perform survival (Kaplan Meier) analysis for time to HCV treatment initiation.

Analysis of adverse event data will primarily be descriptive. Adverse event data will be compared between randomization arms using Fisher's exact Test.

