3.3 Secondary Endpoints

- 1) HCV treatment completion: Proportion of those initiating treatment who complete HCV treatment defined as taking more than 90% of prescribed treatment course by expected end of treatment date.
- 2) SVR 12: Proportion of participants with HCV RNA <15 IU/ml between 10 and 36 weeks after end of treatment in each randomization arm.
- 3) Time to HCV treatment initiation after randomization.

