4.2.8 Randomization

Randomization will occur separately at each OTP. Randomization will take place on day 0 after recruitment screening activities have been performed and the Investigator or designee has determined that the participant is eligible based on information that is available. Day 0 laboratory tests including blood HCV RNA, complete blood count (CBC), comprehensive metabolic panel (CMP), hepatitis B surface antigen (HBsAg), and urine/serum beta HCG, may not be available at the time of randomization and participants may be randomized without this information. Randomization will be built into the study REDCap database. It may not be known at screening whether participants have detectable HCV RNA or not. All participants will be randomized in a 1:1 ratio to test and treat strategy or standard of care referral. Participants who are found to have an HCV RNA that is not detectable, HbsAg positive or a platelet count that is <150,000 will not continue in the study, and will be referred to an offsite location for care.

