Participants in the standard of care arm who do not initiate HCV treatment within 6 months (24 weeks) after randomization and still meet study eligibility criteria upon rescreen will be offered HCV treatment at the OTP site via rollover to the Intervention Arm.

Any participant that does not clear HCV infection will be linked to repeat HCV treatment and care at an offsite HCV treatment location through standard of care. There are approved regimens available to treat patients who do not achieve cure with first line treatment.

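### SVR12 is compared by randomised arm with no cut-off at the 24-week rollover, so cures on rolled-over treatment can count for standard of care

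*Combined protocol and SAP*

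**What the plan says.** - **Rollover.** Section 4.2.9: SOC participants who have not started by 24 weeks and are still eligible on rescreening "will be offered HCV treatment at the OTP site via rollover to the Intervention Arm". Appendix B, note f, adds peer contact, so they receive the strategy under test.
- **SVR12.** Section 3.3, repeated in 7.3.3: "SVR 12: Proportion of participants with HCV RNA <15 IU/ml between 10 and 36 weeks after end of treatment in each randomization arm". The analysis is logistic regression. No limit from randomisation is given.
- **Time to initiation.** Section 7.3.3: "For secondary outcome 3, a time to event outcome, we will perform survival (Kaplan Meier) analysis for time to HCV treatment initiation". No horizon, censoring rule or between-arm test is stated.
- **Population.** Sections 7.2 and 7.3.2 apply mITT to all analyses. The exclusions are undetectable HCV RNA, positive HBsAg and low platelets. Rollover is neither an exclusion nor a reason to censor.
- **Follow-up.** Appendix B schedules HCV RNA at week 56 for anyone untreated at week 12.
- **What is already protected.** The primary endpoint (section 3.2) closes at 12 weeks. Exploratory endpoint 4 (section 3.4) counts SOC starts after crossover, but does not remove them from the secondary endpoints.

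**The concern.** The hypothesis in section 2.2 is that test and treat gives more initiation and more cure than referral to off-site care. SVR12 is the only secondary endpoint that addresses cure. After week 24, SOC participants who are still untreated are offered the intervention, so an uncut comparison sets an immediate on-site offer against referral followed by the same offer later. The better on-site treatment works in rolled-over participants, the smaller the measured benefit. A strategy that truly improves cure over referral could be reported as having no cure benefit, and a cut-off chosen after the data are seen would be post hoc.

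**Working it through.** **1. The plan's own figure.** Section 7.3.1: "With a total sample size of 124 participants, we have 85% power at an alpha of 0.05", for 70% versus 40% initiation. The continuity-corrected two-proportion formula gives exactly 55 per group for 85% power (85.5% at n = 55). Allowing 10% dropout, 55/0.90 = 61.1, rounded up to 62 per group, or 124 in total. The stated figure reproduces. It concerns initiation only.

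**2. Would a rollover cure be observed?** A start near week 25 plus 8 weeks of drug ends near week 33. Week 56 is then 56 - 33 = 23 weeks after treatment, inside the 10-36 week SVR12 window. The scheduled test would capture the cure.

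**3. SVR12.** Inputs from section 7.3.1: 70% intervention starts, 40% SOC starts (range 30-50% across cities). Assumptions not in the documents: the 40%, which has no stated time frame, is read as SOC starts by week 24; 90% of starters are cured in either arm; r is the share of untreated SOC participants who start after rollover; all mITT participants are in the denominator.

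SOC SVR12 = 0.9 × (0.40 + 0.60r). Intervention SVR12 = 0.9 × 0.70 = 63%. If 20% of intervention non-starters also start late, ever-start is 0.70 + 0.30 × 0.20 = 76%, and SVR12 is 0.9 × 0.76 = 68.4%.

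| r | SOC ever-start | SOC SVR12 | Difference, intervention 63% | Difference, intervention 68.4% |
|---|---|---|---|---|
| none (pre-rollover) | 40% | 36.0% | +27.0 | not applicable |
| 30% | 58% | 52.2% | +10.8 | +16.2 |
| 50% | 70% | 63.0% | 0 | +5.4 |
| 70% | 82% | 73.8% | -10.8 | -5.4 |

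With no late intervention starts, the difference is zero when 0.40 + 0.60r = 0.70, so r = 50%. Over the plan's SOC range, break-even is (0.70 - 0.30)/0.70 = 57% at 30% uptake and (0.70 - 0.50)/0.50 = 40% at 50% uptake. A cure rate common to both arms cancels from this. At 85% or 95% cure, the pre-rollover difference is +25.5 or +28.5 points, and the r = 70% difference is -10.2 or -11.4.

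**4. Power for SVR12**, two-sided 0.05, without continuity correction: Φ{[|d| - 1.96√(2p̄(1-p̄)/n)] / √[(p₁(1-p₁) + p₂(1-p₂))/n]}.
- 63% v 36%, n = 55: (0.270 - 0.187)/0.0918 = 0.91, power 82%. At n = 62: (0.270 - 0.176)/0.0865 = 1.09, power 86%.
- 63% v 52.2%, n = 55: (0.108 - 0.185)/0.0937 = -0.82, power 21%. At n = 62, 23%.
- With the continuity correction that reproduces the plan's 85%, subtract 1/55 = 0.018 from the first numerator: 0.065/0.0918 = 0.71, power 76%.

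**5. Time to initiation.** Kaplan-Meier estimates up to week 24 do not depend on later events. Summaries past week 24 were simulated (55 per group, 600 runs, 56-week horizon; intervention starts in weeks 0.5-12, SOC starts in weeks 2-24, rollover starts in weeks 24.5-30; these timings are assumptions). Censored at week 24, the rate ratio is about 3.0 and log-rank power about 98%. Uncensored, the ratio is 1.6 (power 53%) at r = 50%, 1.3 (25%) at r = 70% and 1.03 (5%) at r = 90%. With 20% late starts among intervention non-starters, r = 70% gives 1.5 (43%). A significant result in the wrong direction occurred in at most about 2% of runs. With no late intervention starts, the cumulative curves cross after week 24 only if r exceeds 50%.

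**The case against.** Several points on the other side stand.

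- **Denominator.** The SVR12 definition does not say how people who were never treated, and so have no end of treatment, are counted. If only treated participants counted, rollover would matter little. The all-participants reading is an inference, though a natural one: only secondary endpoint 1 limits itself to people who started.
- **Late intervention starts.** A reader might hold intervention uptake at 70% and conclude that the effect must disappear. Only SOC has a formal rescreen and re-offer, but no expiry of the on-site offer is stated, and Appendix B follows non-starters in either arm to week 56. Late starts soften the dilution.
- **Rollover uptake.** Reversal requires about half or more of a selected group, untreated for 24 weeks and required to re-qualify, to start. The documents give no rate for them. Using the 70% planning rate is an assumption.
- **Time to initiation.** A reader might infer that this endpoint is reversed too. The documents do not support that: estimates to week 24 are intact and no log-rank test, hazard ratio or final proportion is specified.
- **Estimand.** Analysis by randomised arm regardless of rollover is a legitimate treatment-policy comparison. It answers a different question from section 2.2, however, and the plan does not say that it is the intended one.

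Exploratory endpoint 4 lets readers see the crossover starts, but leaves them in SVR12.

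**Conclusion.** The gap is real and should be fixed, but it is confined to secondary endpoints. The primary endpoint closes before rollover, so nothing here supports doubt about the primary result or the stated 85% power.

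For SVR12, rollover cures dilute the comparison and could nullify or reverse it: from +27 points to +11, 0 or -11 at 30%, 50% or 70% rollover uptake, or about +16, +5 and -5 with 20% late intervention starts. This rests on an all-mITT denominator, 40% SOC starts by week 24, 70% intervention starts and 90% cure. The direction of the dilution needs only the denominator and some cures after rollover; its size depends on all of the assumptions.

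For time to initiation, the risk is dilution of any summary carried past week 24. A significant reversal is unlikely.

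**What to change.** In sections 3.3 and 7.3.3:

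1. **SVR12, main comparison.** Put all mITT participants in the denominator. Success is cure after treatment that began within 24 weeks of randomisation and before any rollover, with the same cut in both arms.
2. **Time to initiation.** Censor at 24 weeks in both arms, or at rollover if that comes earlier. The week 24 visit window opens 14 days early, so an earlier date is possible.
3. **After rollover.** Report starts and cures descriptively alongside exploratory endpoint 4. Give the uncut SVR12 comparison by randomised arm as a supplementary analysis.

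The cost is protocol and SAP wording: no added visits, tests or participants, and no change to the rollover offer. The downside is that late starts and their cures, in either arm, leave the main secondary comparison. A site-stratified log-rank test or restricted mean time would be an optional addition and is not part of this correction.

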3.4 Exploratory Endpoints

- 1) Impact of test and treat versus standard of care referral on proportion of participants with change in substance use assessed by self-reported drug use in the preceding 30 days and urine toxicology at recruitment screening, end of HCV treatment, and post-treatment weeks 12, 24, and 36. Participants who do not start HCV treatment will be assessed at weeks 12, 24, and 36 post-randomization.
- 2) Impact of test and treat versus standard of care referral on subsequent substance use disorder treatment engagement-Proportion of expected weekly OTP visits actually attended, based on participant's OTP treatment plan.
- 3) Proportion of patients in the standard of care arm who are not offered treatment within 6 months (24 weeks) of randomization.
- 4) Proportion of patients in the standard of care arm who do not initiate treatment within 6 months (24 weeks) of randomization and subsequently initiate HCV treatment after study cross over to intervention arm.
- 5) Patient reported outcomes, quality of life measures, and patient satisfaction with test and treat model versus standard of care referral will also be assessed.
- 6) Proportion of participants with grade 3 or greater adverse events (AEs) in test and treat model versus standard of care referral.

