6.2.2 Medical Complaints/Adverse Events and Serious Adverse Events

An AE is defined as any untoward medical occurrence in a subject or clinical investigation subject administered a pharmaceutical product and which does not necessarily have a causal relationship with this treatment. An AE can therefore be any unfavorable and unintended sign (including an abnormal

laboratory finding), symptom, or disease temporally associated with the use of a medicinal (investigational) product, whether or not the event is considered causally related to the use of the product.

An AE can result from use of the drug as stipulated in the protocol or labeling, as well as from accidental or intentional overdose, drug abuse, or drug withdrawal. Any worsening of a pre-existing condition or illness is considered an AE. Worsening in severity of a reported AE should be reported as a new AE. Laboratory abnormalities and changes in vital signs are considered to be AEs only if they result in discontinuation from the study, necessitate therapeutic medical intervention, meets protocol specific criteria (see Section 6.3 regarding toxicity management) and/or if the investigator considers them to be AEs.

Adverse event reporting will follow the requirements outlined below. Adverse events will also be recorded and tracked in a safety monitoring database by the investigators. Serious adverse events (SAEs) will be reported to the Institutional Review Board according to IRB guidelines and to AbbVie via the Johns Hopkins University Transplant Oncology and Infectious Diseases Clinical Research Center (TOID CRC).

All Grade 3 or higher and all SAEs related to the use of GLE/PIB in intervention arm or prescribed DAA course in SOC arm will be collected. Thus, AEs and SAEs will only be collected from the time of first DAA dose to 30 days after completion of DAA course.

All Grade 3 or higher AEs and all SAEs will be reviewed by the principal investigator as they occur in a timely manner. All AEs related or possibly related to GLE/PIB will be reported by the site to the TOID CRC within 72 hours of the site being made aware via the REDCap EDC system. All SAEs will be reported to the TOID CRC via the REDCap EDC system within 24 hours of the site being made aware. Notification of all SAEs will be made to AbbVie by the TOID CRC via email within 24 hours of entry into REDCap.

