7.2 Definition for Analysis Populations

All analyses will be conducted with a modified intention to treat approach, which excludes randomized participants who were found on testing to have an undetectable HCV RNA, HBsAg positive or a platelet count <150,000.

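### The adverse event comparison between randomised arms largely tracks treatment uptake, because events are recorded only in participants who start a DAA

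*Combined protocol and SAP*

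**What the plan says.** Four parts of the plan meet here.

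- **Collection.** Section 6.2.2 says that "AEs and SAEs will only be collected from the time of first DAA dose to 30 days after completion of DAA course". Footnote d of the Appendix A schedule agrees. Appendix B, for participants untreated by week 12, has no adverse event row. Section 6.2.2 describes the scope as "All Grade 3 or higher and all SAEs related to the use of GLE/PIB in intervention arm or prescribed DAA course in SOC arm".
- **Endpoint.** Exploratory endpoint 6 in Section 3.4 is the "Proportion of participants with grade 3 or greater adverse events (AEs) in test and treat model versus standard of care referral".
- **Population.** Section 7.2, repeated in Section 7.3.2, says "All analyses will be conducted with a modified intention to treat approach". That set drops participants with undetectable RNA, positive HBsAg or low platelets. It does not drop those who never start treatment, and no separate safety population is defined.
- **Analysis.** Section 7.3.3 says "Analysis of adverse event data will primarily be descriptive" and then "Adverse event data will be compared between randomization arms", by Fisher's exact test.

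Section 7.3.1 plans for 70% initiation with test and treat and 40% with referral, the latter an average over 30-50% by city. Section 4.2.9 offers on-site treatment, by rollover, to referral participants still untreated at 24 weeks. No section says to which group their later events belong.

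**The concern.** A participant who never takes a DAA cannot have a recorded event, yet on the plain reading of endpoint 6 and the analysis set that participant is in the denominator. Each arm's event proportion is then its uptake multiplied by its risk per treated person. Uptake is the primary endpoint and is expected to differ widely, so the two arms can show different event proportions when treatment is equally safe in both.

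This is the only between-arm safety comparison in the plan, and Section 6.2.1 provides for no formal safety monitoring board. A published table of, say, 7% against 4% with a Fisher p-value beside it could be taken as a safety cost of on-site treatment when it reflects only that more people were treated.

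**Working it through.** **Inputs.** Uptake 70% and 40%, referral range 30-50%, 62 randomised per arm and two-sided alpha 0.05 (Sections 7.3.1 and 7.3.2). The risk r that a treated participant has a recorded event is not in the documents. It is assumed equal in both arms and varied.

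**The plan's own figure.** The plan gives no figure for the adverse event comparison. Its primary sample size reproduces: 70% against 40% at 85% power with continuity correction needs 55 per arm, and 55 / 0.90 = 61.1, so 62 per arm and 124 in total. That calculation is not affected by this point.

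**Step 1: who can have an event.** 62 × 0.70 = 43.4 participants with test and treat; 62 × 0.40 = 24.8 with referral.

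**Step 2: expected ratio before rollover.** (0.70 × r) / (0.40 × r) = 0.70 / 0.40 = 1.75 for any r above 0. At 30% referral uptake it is 0.70 / 0.30 = 2.33; at 50% it is 0.70 / 0.50 = 1.40.

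**Step 3: Fisher's test, 62 against 62.** Rejection probabilities were enumerated exactly from two binomials with probabilities 0.70r and (referral uptake) × r.

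| Assumed r | Proportions at 70% vs 40% | Expected participants with an event | Rejects, referral uptake 40% | Rejects, 30% | Rejects, 50% |
|---|---|---|---|---|---|
| 5% | 3.5% vs 2.0% | 2.2 vs 1.2 | 0.7% | 0.9% | 0.5% |
| 10% | 7.0% vs 4.0% | 4.3 vs 2.5 | 3.9% | 6.3% | 2.5% |
| 20% | 14.0% vs 8.0% | 8.7 vs 5.0 | 11.6% | 21.3% | 6.1% |
| 30% | 21.0% vs 12.0% | 13.0 vs 7.4 | 19.7% | 37.3% | 9.3% |

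At 40% referral uptake, nearly all rejections go against test and treat.

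**Step 4: rollover.** Suppose a share x of the untreated 60% in the referral arm start later, their events stay with referral, and test-and-treat uptake stays at 70%. Referral uptake becomes 0.40 + 0.60x.

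- x = 25%: 0.70 / 0.55 = 1.27
- x = 50%: 0.70 / 0.70 = 1.00
- x = 70%: 0.70 / 0.82 = 0.85

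The size and even the direction of the contrast therefore depend on later uptake and on a rule that the plan does not state.

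**Step 5: treated denominator.** With about 43 against 25 starters and equal r, the expected ratio is 1.00. Fisher's test rejects in 1.8%, 2.8%, 3.6% and 3.7% of trials at r = 5%, 10%, 20% and 30%.

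**The case against.** The best defence is that this is a trial of strategies. If the restriction to related events in Section 6.2.2 covers both Grade 3 events and SAEs (the wording is slightly ambiguous), an untreated participant has a true zero for DAA-related events. The all-randomised contrast then estimates the drug-related event burden of each strategy, with randomisation intact. This stands as far as it goes: the number is legitimate if labelled as such. It remains driven by uptake and does not measure risk per treated person, and the plan does not say which of the two is meant.

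The denominator is also partly inferred. Section 7.3.3 gives none for adverse events, and treatment completion is analysed among starters under the same modified ITT clause. But that endpoint names its narrower denominator and endpoint 6 does not.

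The practical reach is limited. The endpoint is exploratory, the analysis is called primarily descriptive, and no decision rule hangs on the p-value.

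Two stronger readings are tempting and not supported. A reader might infer that the test-and-treat arm must show more events. That is true only in expectation and before rollover: at r = 5% and 40% referral uptake it has strictly more participants with an event in 59% of trials, and enough later starts counted to referral would cancel or reverse the gap. A reader might also infer that weekly peer contact inflates event capture in that arm. The peer tasks in Section 4.2.9 are surveys on adherence and food, reminders and support; recording adverse events is not among them.

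**Conclusion.** The point holds in a limited form. As written, the adverse event contrast is determined largely by treatment uptake: an expected ratio of 1.75 at the planning rates before any rollover (2.33 to 1.40 over the referral range), with equal risk per treated person. It falls to 1.27, 1.00 or 0.85 if 25%, 50% or 70% of untreated referral participants start later and their events count in that arm.

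These figures rest on equal r, on the planning uptake for a 12-week endpoint standing in for all DAA starts, and on 62 analysed per arm. At the average 40% referral uptake and an assumed r of 10% or less, the harm is mainly a misleading ratio, since the test rejects in 0.7% (r = 5%) to 3.9% (r = 10%) of trials. False rejection passes 5% at an assumed 20% (11.6%).

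It would go too far to say that the comparison carries no safety information, because burden per randomised person has some meaning for a strategy. The change is worth making but is not critical, and the primary analysis is untouched.

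**What to change.** 1. Define a safety population: participants who took at least one DAA dose.
2. Report endpoint 6 on that denominator, with exposure time from first dose to the end of the collection window, by randomised arm, and with referral participants who start after rollover shown separately.
3. State in which group rollover events count.
4. Drop the between-arm Fisher test. If an all-randomised table is kept, label it as a strategy-level result that depends on uptake and does not measure risk per treated person.

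The cost is wording in Sections 3.4, 7.2 and 7.3.3. No new event collection is needed, and the existing window already requires dose start and end dates in both arms. The downside is that starting treatment is a post-randomisation event, so the comparison among treated participants is not protected by randomisation and must be read as descriptive.
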